9.1.4. Open-Label Treatment Phase

Following completion of DB treatment phase (Week 52 assessments) subjects will continue in OL phase. In OL phase, subjects who received placebo in the DB treatment phase will be randomized to open-label active treatment (JNJ-54861911; Week 52 of DB treatment phase) as described above and in Section 6, Dosage and Administration. Subjects receiving JNJ-54861911 in the DB treatment phase will continue their assigned treatment as open-label in OL phase.

Study medication will be self-administered on site as outlined in Section 6, Dosage and Administration.

During OL treatment phase, the subjects will visit the investigational site at regular time points (morning hours) as indicated in the Time and Events Schedule.

In case of progression to a dementia state ($CDR \geq 1$) during course of the study, the subject may go through the consenting process for which a legally appointed representative may provide a renewed assent or consent, as applicable, in accordance with local regulations.

Subjects entering the OL treatment phase will remain blinded with respect to prior treatment assignment (placebo vs active drug) in the 54861911ALZ2002 study and in the DB treatment phase of this study. During the OL treatment phase, all subjects will have monitoring of safety laboratory tests every 2 weeks for the first 12 weeks, every 4 weeks for the next 12 weeks, every 8 weeks for the next 24 weeks, and every 12 weeks thereafter. The assessments to be performed and the frequency of assessments during the OL treatment phase are described in the following Table.

Assessment/Frequency	Every 2 weeks	Every 4 weeks	Every 8 weeks	Every 12 weeks	Every 24 weeks (*)	Every 48 weeks (*) (#)	Every 96 weeks (*) (#) (¥)
Drug accountability/Treatment compliance				X			
Drug return (previous visit)				X			
Drug Dispensing				X			
Physical and Neurological examination						X	
Body Weight						X	
12 Lead ECG				X ^{a,£}	X [£]		
Body Temperature					X		
Supine and standing vital signs (systolic and diastolic blood pressure and pulse)				X			
Clinical safety laboratory assessments – hematology, serum chemistry – under fasted conditions, when feasible	X ^β	X ^γ	X ^δ	X ^ε			
Clinical safety laboratory assessments – urinalysis – under fasted conditions, when feasible					X		
Dermatological Examination						X	
Ophthalmological Examination [§]						X	
OCT (at sites where OCT is available)						X	
C-SSRS (since last visit)				X			
RBANS					X		
MMSE						X	
CFI					X		
CDR						X	
Blood sample collection for plasma JNJ-54861911 concentrations (predose)					X ^{∃,£}		
Blood sample collection for PD/biomarkers (predose)					X [∃]		
CSF sample collection (~12 mL) by single lumbar puncture for PK/PD/biomarker assessment.							X
MRI						X	
Adverse Event and Concomitant Medication				X			

(*) In addition to the assessments performed every 12 weeks. (#) In addition to the assessments performed every 24 weeks. (¥) In addition to the assessments performed every 48 weeks. (§) An ophthalmological examination will only be performed in subjects who had completed the parent study, ALZ2002, if: 1) if there was an abnormality present at the screening/baseline examination; 2) if the investigator detects new ophthalmological findings or visual symptoms; 3) if OCT reveals new findings. The ophthalmologic examination should be performed by the same ophthalmologist who completed the initial ophthalmologic examination at screening/baseline; (∃) predose; (£) 2 to 4 hours postdose; (α) only during the first 12 week visit of the OL treatment phase. (β) assessments performed every 2 weeks for 12 weeks (> Week 52 and ≤ Week 64). (γ) assessments performed every 4 weeks for 12 weeks (> Week 64 and ≤ Week 76). (δ) assessments performed every 8 weeks for 24 weeks (> Week 76 and ≤ Week 100). (ε) assessments performed every 12 weeks after Week 100.

In the OL treatment phase (>52 weeks) it is intended to collect if possible on-treatment CSF samples every 96 weeks until study completion. Subjects may opt not to have these punctures being performed.

For subjects enrolled in this study, subjects will continue study treatment (in the OL phase):

- until registration of JNJ-54861911
- until emerging safety issues arise as determined by the DRC that would warrant termination of the study
- until subject withdraws consent or other reasons for withdrawal as defined in Section 10.3.

Upon decision to stop study participation for any of the reasons described above subject will be asked to return to the investigational site to hand in their study medication. Drug accountability will be performed. No new medication will be dispensed.

In addition subjects will be asked to complete the End-Of-Treatment Visit as described in Section 9.1.5, End-of-Treatment Visit (Follow Up Visit).

9.1.5. End-of-Treatment Visit (Follow Up Visit)

An End-of-Treatment visit (or phone call) for a safety assessment should take place approximately 30 days after the last dose of study drug. This will consist of at least a review of Adverse Events and concomitant medication and C-SSRS assessment (since the last visit). The study is considered completed with the last End-of-Treatment safety assessment for the last subject participating in the study or upon a decision by the sponsor to terminate the study.

Investigators may recontact the subject to obtain long-term follow-up information to determine the subject's safety or survival status (refer to Section 16.2.3, Informed Consent).

9.2. Safety Evaluations

During the treatment phases regular safety assessments will be performed as listed in the Time and Events Schedule. These safety assessments include but are not limited to: vital signs, ECG, physical and neurological examination, adverse events, safety labs, suicidality risks (C-SSRS), dermatologic and ophthalmologic examinations, and MRI.

The DRC may decide to reduce, eliminate or even increase frequency over time of specific safety assessments in case (newly obtained) data collected in this extension study or from ongoing or future studies would support this decision.

Details regarding the DRC are provided in Section 11.7.

Any clinically relevant changes occurring during the study must be recorded on the Adverse Event section of the CRF.

Any clinically significant abnormalities persisting at the end of the study/early withdrawal will be followed by the investigator until resolution or until a clinically stable endpoint is reached.

9.2.1. Adverse Events

Adverse events will be reported by the subject (or, when appropriate, by a caregiver, surrogate, or the subject's legally acceptable representative) for the duration of the study. Adverse events will be followed by the investigator as specified in Section 12, Adverse Event Reporting.

9.2.2. Colombia Suicide Severity Rating Scale (C-SSRS)

Consistent with regulatory guidance, any occurrence of suicide-related thoughts and behaviors will be assessed. An interview to assess the risk of suicidal ideation and behavior will be conducted at the time points listed in the Time and Events Schedule.

The C-SSRS is a measure of the spectrum of suicidal ideation and behavior that was developed in the National Institute of Mental Health Treatment of Adolescent Suicide Attempters Study to assess severity and track suicidal events through any treatment⁴⁸. The C-SSRS is a clinical interview providing a summary of both ideation and behavior that can be administered during any evaluation or risk assessment to identify the occurrence and intensity of suicidal thoughts and suicidal behaviors. It can also be used during treatment to monitor for clinical worsening.

If a suicide-related thought or behavior is identified at any time during the study, a thorough evaluation will be performed by a study physician, and appropriate medical care will be provided.

9.2.3. Vital Signs

Vital signs (body temperature, pulse/heart rate, blood pressure) will be collected at the time points indicated in the Time and Events Schedule.

9.2.4. Electrocardiogram

Twelve-lead ECGs will be collected at the time points listed in the Time and Events Schedule.

At all-time points, triplicate ECGs are required, i.e., 3 individual ECG tracings should be obtained as closely as possible in succession, but no more than 2 minutes apart. The full set of triplicates should be completed in less than 4 minutes.

During the study, the clinical investigator will review the ECG for immediate management and to mark abnormalities. A description of the overall assessment (i.e., normal or abnormal plus reason) will be made and a copy of the trace will be placed with the source data.

All ECGs will additionally be transmitted to be read and interpreted by a central reader appointed by the sponsor.

9.2.5. Physical and Neurological Examination

The study investigator or other authorized and appropriately qualified designee will perform the physical and neurological examinations, including vibration sense (by use of a tuning fork).

Newly presenting ophthalmological findings or visual symptoms will be assessed by the investigator, and if deemed medically relevant, the subject will be referred to the ophthalmologist for evaluation.

Body weight will be measured as per the Time and Events Schedule.

The neurological examination will assess at minimum cranial nerves, motor system, sensory function and coordination.

9.2.6. Dermatologic Examination

Subjects will undergo a comprehensive skin examination performed by a dermatologist at the time points listed in the Time and Events Schedule to detect the presence of skin lesions or depigmentation. A digital photograph of the frontal scalp, open eyes, and eyebrows will be collected to monitor for dermatological changes. This is an essential requirement of the safety monitoring in the trial.

Whenever a skin lesion not previously documented is reported by the study subject or the investigator, in addition to a dermatological exam by the dermatologist, digital images of the lesion will be acquired at the time the lesion is discovered and at follow-up visits with a frequency which is deemed appropriate by the sponsor of the study. Duration of follow-up of newly documented skin lesions or depigmentation might extend beyond the treatment period, as judged adequate by the sponsor to ensure the safety of subjects in this study.

Comparison to the dermatological examinations performed in 54861911ALZ2002 study will be made if applicable.

9.2.7. Optical Coherence Tomography and Ophthalmologic Examination

Both the ophthalmologic examination and OCT will be carried out only in those subjects who had these in 54861911ALZ2002 study.

The ophthalmologic examination will include funduscopy and slit lamp examination, and testing of acuity and intraocular pressure, and will be performed at the time points listed in Time and Events Schedule.

OCT will be performed in all subjects at sites where OCT is available at the time points indicated in the Time and Events Schedule.

A baseline (Day 1 [predose or earlier]) OCT and ophthalmologic examination will be conducted only if no adequate assessments were obtained in 54861911ALZ2002 study within 9 months of first dosing in this study. Otherwise the assessment performed in 54861911ALZ2002 study will serve as baseline. Baseline assessments in this study may be performed during screening for logistical reasons.

During the treatment phase, an ophthalmologic examination, as described above, will only be performed at the time points indicated in the Time and Events Schedule if: 1) if there was an

abnormality present at the initial examination at screening/baseline; 2) if the investigator detects new ophthalmological findings or visual symptoms during a physical examination; 3) if OCT reveals new findings.

At the times of follow-up general physical examinations indicated in the Time and Events Schedule, newly presenting ophthalmological findings or visual symptoms will be assessed by the same qualified person who completed the screening visit. If deemed medically relevant, the subject will be referred to the ophthalmologist for further evaluation.

The on-treatment ophthalmologic examinations should be performed by the same ophthalmologist who completed the initial ophthalmologic examination at screening/baseline in the extension study or under the parent protocol.

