3.3. Interim Analysis of Data

No prespecified interim analysis of unblinded data during the DB treatment phase is planned by the clinical team. However, depending on the recruitment, or in support of regulatory filings for upcoming studies, or for any other reason the Sponsor deems necessary, an unblinded review of safety and biomarker data prior to the last subject's completion of the DB treatment phase might be conducted by an internal Interim Analysis Committee. If any such review is conducted it will be documented in an Interim Analysis Committee charter prior to the unblinding. The constitution of the Interim analysis committee will be documented in the Interim Analysis Committee charter and may include Sponsor study team members.

As noted in Section 5, when the parent study (eg, 54861911ALZ2002 and potential future Phase 1b and 2 studies) is completed and its clinical database is closed, the randomization codes from the parent study will be released to the sponsor study team. Thus, the sponsor will be unblinded at that time, but the investigator and subjects will continue to be blinded to treatment during the DB treatment phase, until the last subject has completed that phase, and the database from that phase has been reviewed, corrected as necessary, and locked. At that point, the sponsor will perform analyses of key safety, biomarker, and efficacy variables, as detailed in a prespecified statistical analysis plan.

Following the sponsor's review of these analyses, information on an individual subject's treatment allocation during the DB phase will be made available upon request by the investigator. As subjects that remain in the study will all be receiving open label JNJ-54861911

at that time, and as no change or alteration of the locked database from the DB phase will be possible, there should be no bias introduced by this measure.

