4.1. Inclusion Criteria

Each potential subject must satisfy all of the following criteria to be enrolled in the study.

1. Criterion modified per amendment.
 - 1.1 Subjects in the early AD spectrum at time of enrollment meeting all pertinent inclusion and exclusion criteria of the parent protocol, must have very recently completed their treatment in a Phase 1b or Phase 2 JNJ-54861911 clinical study (e.g., 54861911ALZ2002) under the parent protocol. Enrollment in this study should be completed (Day 1 of DB treatment phase) as soon as possible, but within 6 weeks, following completion of their treatment period under the parent protocol. If not defined under the parent protocol, completion of the treatment period is defined as having completed all study related procedures of the last visit of the treatment period under the parent protocol. A screening phase of up to 12 weeks may be allowed following written approval of the Sponsor.
2. Subject must be willing and able to adhere to the prohibitions and restrictions specified in this protocol.
3. Criterion modified per amendment.

- 3.1 Each subject must sign an informed consent form (ICF) indicating that he or she understands the purpose of and procedures required for the study and are willing to participate in the study.
4. Subjects must have a reliable informant (relative, partner, or friend). The informant must be willing to participate as a source of information and has at least weekly contact with the subject (contact can be in-person, via telephone or other audio/visual communication). The informant must have sufficient contact such that the investigator feels he/she can provide meaningful information about the subject's daily function. If possible, an alternate informant meeting these criteria who can replace the primary informant should be identified prior to randomization.

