that dosage. Subjects receiving placebo in the DB treatment phase will be randomized with equal chance to either 5 mg q.d or to 25 mg q.d. Neither the randomization number nor the fact that a subject was randomized for OL phase will be known to the investigator, thus allowing the blind to be maintained while DB treatment phase is still ongoing.

The total number of subjects on placebo to be randomized to active treatment in this study will be determined by the number of subjects enrolling who previously were allocated to placebo in 54861911ALZ2002 study.

Central randomization will be implemented in conducting OL phase of this study for subjects previously receiving placebo. Central randomization minimizes the imbalance in the distribution of the number of subjects across treatment. Based on the algorithm, the IWRS will assign a unique treatment code, which will dictate the treatment assignment and matching study drug kit for the subject.

Central randomization will be used to avoid bias in the assignment of subjects to treatment, to increase the likelihood that known and unknown subject attributes (e.g., demographics and baseline characteristics) are evenly balanced across treatment groups.

During the DB treatment phase (placebo-controlled), both the investigator and the subject will be blinded to reduce subjective influences on safety and tolerability data.

Blinding

The investigator will not be provided with randomization codes for the parent protocol (54861911ALZ2002 study) or the randomization numbers for this study until all subjects of the parent protocol have completed DB treatment phase and subsequent database lock or freeze has occurred. The codes will be maintained within the IWRS, which has the functionality to allow the investigator to break the blind for an individual subject.

Under normal circumstances, the blind should not be broken by the investigator until all subjects from the 54861911ALZ2002 study enrolled in this study have completed DB treatment phase of the study and the DB treatment phase database for those subjects is finalized.

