9.2.8. Magnetic Resonance Imaging

All subjects will receive an MRI in this study at the time points indicated in the Time and Events scheduled for primarily safety reasons.

An additional baseline MRI may be collected (during screening or Day 1) in case subjects are enrolled from future JNJ-54861911 studies who did not obtain an adequate MRI under the parent protocol 6 months prior to first dosing in this study. For subjects who participated in study 54861911ALZ2002 no baseline MRI scan is to be collected as an MRI was collected at Month 6 under the parent protocol.

Collection of MRI data is primarily for safety reasons. MRI scans will be collected during DB treatment phase (up to and including Week 52 [Month 12]) and OL treatment phase (annual). Additional MRI scans may be collected based on emerging safety data (e.g., ARIA-E or H) with a frequency as recommended by the DRC.

Imaging sequences for all pre-specified protocol MRI studies will consist of an identical set of pulse sequences, including FLAIR and T2* sequences, as described in the MRI imaging manual.

Global and regional brain volumes and regional cortical thickness will be derived from the volumetric MRI sequence and will include both cross sectional absolute measurements and longitudinal volume change. The regional volumes and regional cortical thicknesses that will be chosen for this study will include those anatomical areas that are most affected in AD.

All MRI data collected (screening and on treatment) will be sent to a core imaging lab for quality control purposes and for data management, image processing, data analysis, and archiving.

MRI image evaluation will be performed by a core imaging lab.

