11.2. Sample Size Determination

The study is not powered according to statistical calculations. The number of subjects enrolled will depend on the number of subjects from other JNJ-54861911 studies who are willing to enroll in this extension study.

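### Who receives scheduled OCT and eye examination, and when the investigator's blind ends, are each stated in conflicting ways: some passages are tied to ALZ2002 and others are not

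*Protocol*

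**What the plan says.** **Population.** Inclusion criterion 1.1 (Section 4.1) says subjects "must have very recently completed their treatment in a Phase 1b or Phase 2 JNJ-54861911 clinical study (e.g., 54861911ALZ2002) under the parent protocol", so ALZ2002 is only an example. Section 3.1 also admits completers of future Phase 1b or Phase 2 studies. Section 9.2.8 provides for a baseline MRI "in case subjects are enrolled from future JNJ-54861911 studies" without an adequate recent scan.

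**Eye monitoring.** The first sentence of Section 9.2.7 reads "Both the ophthalmologic examination and OCT will be carried out only in those subjects who had these in 54861911ALZ2002 study". The third paragraph reads "OCT will be performed in all subjects at sites where OCT is available". Section 9.1.3 (Day 1, Week 24, Week 52) limits both assessments to ALZ2002 completers. In Section 9.1.4 the table note limits the open-label eye examination to ALZ2002 completers, but the OCT row carries only the site-availability condition. Time and Events footnotes e, m and r contain no ALZ2002 limit.

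**Blinding.** Section 5 says that normally "the blind should not be broken by the investigator until all subjects from the 54861911ALZ2002 study enrolled in this study have completed DB treatment", and adds that the double-blind data for those subjects must be final. Section 3.3, repeated in Section 11.6, says "the investigator and subjects will continue to be blinded to treatment during the DB treatment phase, until the last subject has completed that phase". Both sections also require a locked database for the phase before the blind ends.

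**The concern.** Long-term safety is the primary objective. Treatment-emergent ophthalmologic events are adverse events of special interest (Section 12.3.4), and Section 11.5 presents eye and OCT results by treatment group. If sites resolve the conflicting eye passages differently, whether a subject was examined on schedule becomes partly a matter of interpretation, and examined and unexamined subjects are mixed in that output.

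The blind matters because adverse-event causality, the C-SSRS and the CDR are rated by site staff during the placebo-controlled year. A milestone defined by one parent study can be reached while subjects from another parent are still in that year.

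**Working it through.** No arithmetic applies. Section 11.2 says "The study is not powered according to statistical calculations", and neither contradiction rests on a figure. The check is to take each kind of subject through the passages.

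**Scheduled OCT at a site that has the equipment**

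| Passage | ALZ2002 completer, OCT done there | ALZ2002 completer, no OCT there | Entrant from another parent |
|---|---|---|---|
| 9.2.7, first sentence | yes | no | no |
| 9.1.3, Day 1, Weeks 24 and 52 | yes | yes | no |
| 9.2.7, third paragraph | yes | yes | yes |
| Time and Events, footnote r | yes | yes | yes |
| 9.1.4, OCT row | yes | yes | yes |

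Only the first column is consistent. The second shows that the conflict does not depend entirely on other parent studies. Section 9.2.7 conditions on having had the assessment in ALZ2002, whereas Section 9.1.3 conditions on having completed ALZ2002. The baseline rule in 9.2.7 adds to this: it calls for a baseline OCT and eye examination when ALZ2002 supplied no adequate one within 9 months, which the first sentence rules out for anyone who had none there.

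**Eye examination.** The difference is narrower. During treatment the examination is conditional for every subject: abnormality at baseline, new findings or symptoms, or new OCT findings (footnote m and Section 9.2.7). For an entrant from another parent who meets a condition, footnote m gives the examination, while Section 9.1.3, the note in Section 9.1.4 and the first sentence of 9.2.7 do not.

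**Blind.** Let A be the date when all ALZ2002 subjects have completed the double-blind phase and their data are final. Let L be the date when the last subject of any origin has completed it and the database is locked.

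- Section 5, code release and blind-break sentences: milestone A.
- Sections 3.3 and 11.6: milestone L.
- Section 11 also places the double-blind lock after all subjects have completed the phase, which agrees with L.
- If every double-blind subject comes from ALZ2002, A and L rest on the same subjects and nothing is lost.
- If a subject from another parent is still in the phase at A, then L is later than A. Section 5's bar has run out and it names no later date, while Sections 3.3 and 11.6 still require the blind.

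Sections 3.3 and 11.6 argue that releasing allocation introduces no bias because everyone remaining is then on open-label drug and the double-blind data can no longer change. Both premises are guaranteed at L. At A neither is guaranteed for an entrant from another parent.

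**The case against.** The strongest reply is that the affected group may not exist. At the Amendment 6 cutoff, ALZ2002 and the two 4-week studies in the target population were complete. The only other ongoing study was ALZ2003, a Phase 2b/3 trial not named as a parent. Entry must follow within 6 weeks, or up to 12 with sponsor approval. Section 11.5 lists ALZ1005 among preceding studies but does not say its subjects enter directly. This stands as a limit on size. It does not remove the conflict for an ALZ2002 completer who had no OCT there, and Sections 3.1, 3.3 and 9.2.8 still plan for other entrants.

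A reader might infer that other entrants can be unblinded for up to their whole 52-week double-blind year. The documents do not support that. The blind-break sentence in Section 5 refers to the data of those subjects, which reads as a lock for that cohort. The codes it names are those of ALZ2002. The last paragraph of Section 5 keeps investigators and subjects blinded during the double-blind phase, and other unblinding is for emergencies only. The 52 weeks is a worst case on a literal reading. What remains is a missing milestone in Section 5 and a disagreement with 3.3 and 11.6.

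A reader might also infer that other entrants go without eye care. They do not. Section 9.2.5 requires investigator assessment of new visual findings or symptoms, with referral if medically relevant, for everyone, and Section 12.3.4 reporting is general. Any restriction runs by parent study and not by arm, so nothing in the text makes ascertainment differ between arms within a parent. OCT is in any case limited to equipped sites.

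Finally, the amendment history shows that the ALZ2002 eye limit was added on purpose. That explains the restrictive sentences but does not reconcile them with the unrestricted ones that remain.

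**Conclusion.** Both contradictions are in the current text. Whether an entrant from another parent, or an ALZ2002 completer without OCT in that study, receives scheduled OCT depends on the passage a site follows. Section 5 sets the end of the investigator's blind by ALZ2002 subjects alone, against the last-subject rule in Sections 3.3 and 11.6, and the no-bias statement holds as written only under the latter.

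The size cannot be computed. The number of entrants from other parents is not given and may be zero, and the number of ALZ2002 completers without OCT there is not given either. The blinding point matters only if a subject from another parent is in the double-blind phase when the ALZ2002 subjects finish. The documents show neither actual mid-phase unblinding nor a loss of all eye surveillance. Correction is still worthwhile: the study is primarily about safety, the wording change is small, and it protects both the blind and consistent ascertainment.

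**What to change.** In Section 5, replace the ALZ2002 milestone in both the code-release and the blind-break sentences with that of Sections 3.3 and 11.6: the last subject in the double-blind phase has completed it and the double-blind database is locked.

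Reconcile Sections 9.1.3, 9.1.4 and 9.2.7 with Time and Events footnotes e, m and r, so that who receives scheduled eye examination and OCT is stated once and cross-referenced elsewhere. Which rule to adopt is for the sponsor and its clinical advisers.

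Narrowing inclusion criterion 1.1 to ALZ2002 completers is a separate design preference and is not needed to resolve either conflict.

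The cost is amendment wording and, if subjects from another parent do enter, possibly a later release of allocation to investigators.
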